The primary purpose of this amendment is to present [REDACTED] the resultant modifications to the protocol, and to adjust the sample size to enable program decision making at the completion of Part A. In addition, editorial revisions were made to clarify the terminology of the oral nutritional supplement and to improve understanding in other areas of the text.

[REDACTED]

The results from Part A will be used for strategic decision making within the bimagrumab program. To ensure an adequate sample size will be available for the interim analysis following Part A, the total number of patients randomized has been increased from 150 to 196. The additional patients will increase the predicted power for interpretable results based on the original calculation, using estimates of the minimum and maximum variability expected in the SPPB data.

The term “protein supplement” was used in prior versions of the protocol to describe a nutritional supplement that contained a certain amount of dietary protein and other macro- and micronutrients. In order to eliminate confusion by using more universally understood terminology, “protein supplement” has been replaced with “oral nutritional supplement” to more accurately reflect the product intended to be consumed by the patient. The actual product used should not be changed.

Changes to the protocol

[Assessment Schedule](#), [Section 3.1](#) Study design, [Section 6](#) Visit assessments [Section 13](#) Appendix 1: Sample log table – all matrices,

- Clinical chemistry samples added at Week 3, 5, and 9.

[Protocol synopsis](#)

- Updated to reflect changes throughout the protocol.

[Section 3.1](#) Study design, [Section 3.5](#) Purpose and timing of interim analyses/design adaptations, [Section 4](#) Population, [Section 5.2](#) Treatment arms, [Section 5.5](#) Treating the patient

- Total number of patients enrolled until the end of Part A was updated to 196, to include 100 patients randomized to BYM338 700 mg and 60 patients randomized to placebo.

- Total number of patients to be enrolled in Part B and randomization ratio of Part B was clarified.
- Total number of patients to be enrolled in the entire study (Parts A and B) updated to 339.
- Study Flow Diagram (Figure 3-2) clarified.

Section 3.1 Study design

- Updated to remove reference to electronic diaries.

Section 3.1.2 Interim Analysis and Section 9.4.2.1 Analysis for part-A

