Revisions to the inclusion and exclusion criteria should broaden participant eligibility without compromising safety. Minimum body weight will be lowered from 40 kg to 35 kg to accommodate the normal lower body weight of older adults in Asian countries. Particular conditions often seen in older adults (e.g., depression) that are well-managed may be considered if the patient is able to comply with all study procedures. In addition, the Mini Mental State Examination (MMSE) score for inclusion into the study has been lowered from 24 to 21 to include patients with mild cognitive impairment who are able to comply with study activities and to accommodate a limitation of the instrument in people with lower education levels, experienced in several countries. Other criteria that were overlapping or not clearly described have been clarified.

[REDACTED]

[REDACTED] In line with decreasing the study burden for patients, the frequency of efficacy [REDACTED] assessments has also been reduced.

[REDACTED]

At the time of this amendment, approximately 65 patients have been enrolled in the study. All patients enrolled in the study prior to this amendment will continue on the treatment arm they were randomized to, but will be switched to the new assessment schedule at their next study visit (assessment schedule for Parts A and B are the same). Patients who have undergone a baseline echocardiogram under a prior version of the protocol will have a follow up assessment at study end of treatment (EOT). All patients who receive study drug will be included in the safety and efficacy analyses as described in the analysis plan in this protocol.

Changes to the protocol

Title Page

- Study branding (InvestiGAIT) added to study title.
- Removal of ‘parallel group’ in line with the new study design.

Protocol Synopsis

- Amended to reflect changes throughout the protocol.

Assessment Schedule

- Elimination of the following assessments:
 - Echocardiography (will only be performed at EOT for patients enrolled prior to this amendment who have received a baseline scan). A footnote (#12) has been added to specify the same.
 - FSH, LH and Sex hormone-binding globulin (SHBG)
 - Coagulation parameters
 - [REDACTED]
 - [REDACTED]
 - [REDACTED]
 - [REDACTED]

- Reduction in frequency of the following assessments:
 - Physical examination (removed at visits 102, 103, 105 and 106).
 - Height (removed at EOS).

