3.1 Study design

[figure not shown]
This Phase IIb study is a two-part, randomized, double-blind, placebo-controlled study design with approximately 339 older adults with sarcopenia assigned to one of four treatment groups: placebo, bimagrumab 70mg, bimagrumab 210mg, or bimagrumab 700mg,

The study will consist of a 20-day screening period followed by a 28-day run-in period, and a 24-week treatment period followed by a 4 week follow-up period. During the run-in period, all patients will be introduced to [REDACTED] the performance-based endpoints. Towards the end of the run-in period, patients will be re-assessed for eligibility (utilizing the baseline eligibility criteria) and qualified patients will enter the treatment phase to receive six monthly doses of assigned study drug. Patients randomized prior to implementation of protocol amendment v02 will remain on their assigned treatment, but will be switched to the new assessment schedule at their next scheduled visit. [REDACTED]

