3.1.1 Part A

Patients will be enrolled and randomized to receive either bimagrumab 700 mg or placebo (see Figure 3-1), until approximately 100 patients will have been enrolled in the bimagrumab arm and 60 patients in the placebo arm. At this point, recruitment into the study will be paused until Part A is completed and an interim analysis conducted.

Figure 3-1 Study Design: Part A

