3.2 Rationale for study design

The two-part, randomized, double-blind, placebo-controlled design of this phase IIb study will allow a comparison of repeat dosing of three dose regimens of bimagrumab and placebo on changes in muscle quantity and patient physical function in a population of older adults with sarcopenia.

Patient population

The study population will be comprised of men and women aged 70 years or older with sarcopenia and muscle-associated slow gait speed (GS). The population enrolled in this study should reflect the general heterogeneity of elderly people with low skeletal muscle mass and mobility limitation with regard to co-morbidities, polypharmacy, physical functional status, physiological reserve, and physical activity patterns. Data on drug safety, tolerability, [REDACTED] and pharmacodynamics from this design and population, should provide an assessment of possible beneficial or adverse effects of bimagrumab in the larger global population of elderly adults with similar co-morbidities, functional status and mobility limitations. The exclusion criteria aim to omit individuals whose health condition(s) or status could put them at unwarranted safety risk from participation in study activities; those patients in whom their muscle related dysfunction is not the primary reason for low functional capacity; patients likely not to improve due to non-muscle issues, e.g. unmanaged osteoarthritis pain; or patients with conditions that could confound the study objectives. To better clarify the potential effects of bimagrumab and to minimize within and between country differences in standard of care of older adults with mobility limitations, all study participants will receive oral nutritional supplements (ONS) and vitamin D and participate in a personalized exercise program.

Design

A randomized, placebo-controlled, double-blind design will be used to ensure the comparison of active vs. placebo treatments. Due to the subjective and effort-based nature of many study endpoints (e.g., AEs, SPPB, 6MWT, [REDACTED], [REDACTED]), randomization to treatment and investigator and patient blinding will minimize the potential bias of patients and assessment personnel on key safety and performance-based endpoints.

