The original four arm parallel design with three dose levels will become a two part study as of protocol amendment v02, to better address key study goals and to reduce the number of patients potentially exposed to an ineffective therapy until there is more evidence that bimagrumab is useful in treating sarcopenia. This study is the first to assess the SPPB in patients with sarcopenia administered bimagrumab. Therefore, Part A will determine the effect of the highest dose level (700 mg) of bimagrumab on total SPPB score compared to placebo in this population. At the completion of Part A, an interim analysis will be performed to determine efficacy and a sample size re-estimation to confirm original enrollment plan.

[REDACTED] Patients randomized to 70 mg and 210 mg bimagrumab before amendment v02 [REDACTED] will complete the study following the assessment schedule of this amendment and their data will be combined with other patients who receive the same dose level in Part B. Completion of Parts A and B will achieve the same objectives as the original design, just in a staggered manner.

Randomization will be used to account for the expected heterogeneity of the geriatric sample population and to minimize selection, age, gender and baseline differences between groups. It is expected that patients administered bimagrumab will demonstrate a greater increase in muscle mass (LBM and ASMI) after receiving the drug compared to patients receiving placebo and that this increase in muscle will translate into an increase in physical function seen as an improvement in the SPPB score and other outcomes.

Outcome variables

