5.5 Treating the Patient

5.5.1 Patient numbering

Patient number

Each patient screened is assigned a unique patient number. The screening number is a combination of a four digit center number, which is provided by Novartis, and a three digit sequential number allocated by the investigator, starting with 001. Therefore, if the center number is 1001, the patient numbers will be assigned such as 1001001, 1001002, etc. in ascending order. If the center number is 1002, the patient numbers will be assigned such as 1002001, 1002002, etc.

The investigator or his/her staff will contact the IRT and provide the requested identifying information for the patient to register them into the IRT.

Patients can be re-screened and should be assigned a new patient number.

Randomization number

If the patient is deemed eligible for the study following Baseline and will commence the dosing, a randomization number will be assigned using an interactive response technology (IRT) system. Once assigned to a patient, a randomization number will not be reused.

5.5.1.1 Randomization scheme before protocol amendment v02:

All eligible patients were randomized [REDACTED] (bimagrumab 700mg : bimagrumab 210mg : bimagrumab 70mg : Placebo) ratio in 4 treatment arms. [REDACTED]

5.5.1.2 Randomization scheme for Part A:

Following protocol amendment 02, for Part A, patients will be randomized into bimagrumab 700 mg and placebo using a [REDACTED] scheme. [REDACTED]

[REDACTED] No randomization into lower dose groups (bimagrumab 70mg and bimagrumab 210 mg) will occur in Part A.

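### Do the 70 mg and 210 mg comparisons lack a randomization-period term, given that those arms take no patients in Part A?

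*Protocol*

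**What the plan says.** - Amendment 3 gives the counts at the end of Part A: the number "enrolled until the end of Part A was updated to 196, to include 100 patients randomized to BYM338 700 mg and 60 patients" on placebo. Section 3.1 sets the total at "approximately 339 older adults with sarcopenia assigned to one of four treatment groups".
- Section 5.5.1.2: "No randomization into lower dose groups (bimagrumab 70mg and bimagrumab 210 mg) will occur in Part A". Low-dose patients therefore come from the four-arm scheme before v02 or from Part B. The Amendment 2 rationale puts that early cohort in scale: "At the time of this amendment, approximately 65 patients have been enrolled in the study".
- Section 3.1.1: once the Part A numbers are reached, "recruitment into the study will be paused until Part A is completed and an interim analysis conducted".
- Section 3.2, on patients given 70 or 210 mg before v02: "their data will be combined with other patients who receive the same dose level in Part B". It also announces "a sample size re-estimation to confirm original enrollment plan" at the interim analysis.
- Section 3.1.3 keeps the assessments the same in Parts A and B. Section 9.4.4 shows run-in SPPB as a covariate in the supportive model and three unadjusted comparisons with placebo.
- The text of the Part B primary model, the start of the supportive model, both allocation ratios and the body of Table 9-5 are blacked out.

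**The concern.** Randomization balances arms only among patients who could have been allocated to any of them. Here the allocation changes twice. Placebo and 700 mg fill mainly before the pause, and the low doses mainly after it. If the final analysis treats each arm as one homogeneous group, a change in measured response between Part A and Part B acts like a dose effect.

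There are conceivable routes for such a change. Section 3.2 itself warns of bias "Due to the subjective and effort-based nature of many study endpoints". Part B follows an unblinded interim analysis at which Table 16-1 lets some sponsor roles see group-level results. The share of patients on active drug may also be higher in Part B. Since Part B exists to place 70 and 210 mg between placebo and 700 mg, a distorted dose-response curve would matter. The visible planning tables appear to use pooled arms, which invites the conclusion that the analysis does too.

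**Working it through.** **1. Reproduce the planning figures.** Optimal contrasts are c_i ∝ n_i(μ_i − μ̄), with μ̄ weighted by n. Take n = 60:60:60:85 (placebo, 70, 210, 700 mg) and a linear shape. The mean dose is (60·70 + 60·210 + 85·700)/265 = 287.9. The raw terms are 60·(−287.9), 60·(−217.9), 60·(−77.9) and 85·412.1. Scaled to unit length they are −0.4168, −0.3155, −0.1128 and 0.845, as in Table 9-4. An Emax shape with ED50 105 and an exponential shape with delta 300 reproduce the other eight entries. The minimum trend power over the three shapes (one-sided 2.5%, 261 df) matches all 37 cells of Tables 9-6 and 9-8 within 0.004. The planning therefore pools arms without a period term. It shows no baseline covariate either, although Section 9.4.4 uses one, so planning tables do not reveal the model's factors.

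**2. Layout.** Low-dose patients before v02: 196 − 100 − 60 = 36. Part B: 339 − 196 = 143. Assume 18 per arm before v02 (72 in all, close to the 65 reported when Amendment 2 was written). Part A then adds 42 placebo and 82 on 700 mg. The Part B ratio is not visible. The Table 9-4 weights imply totals of about 77:77:77:109, hence Part B of about 17:59:59:9. Placebo:70:210:700 ratios from 1:1:1:1 to 1:4:4:2 were also tried.

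**3. Weight of a shift if arms are pooled.** This is the difference between two arms in the share of patients coming from the shifted period.

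| Part B split | Part B shift, 70 mg vs placebo | Part B shift, 70 vs 700 mg | Pre-v02 shift, 70 mg vs placebo |
|---|---|---|---|
| implied | 59/77 − 17/77 = 0.55 | 59/77 − 9/109 ≈ 0.69 | 0.00 |
| 1:4:4:2 | 0.56 | 0.54 | 0.01 |
| 1:1:1:1 | 0.29 | 0.40 | 0.15 |

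The documented changes in eligibility and schedule came at v02. A pre-v02 shift is the one that nearly cancels in low dose versus placebo. The large weights belong to a Part A to Part B shift, for which the protocol documents no change in assessments.

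**4. Trend error under assumed drift, arms pooled, 265 analysed.** A downward Part B shift of 0.25 SD with no drug effect gives 10.7% (implied), 6.6% (1:4:4:2) and 5.7% (1:1:1:1). At 0.10 SD the range is 3.5-4.4%. An upward shift of 0.25 SD makes the trend test conservative (1.0-1.7%), but a false benefit of 70 or 210 mg over placebo rises from 2.5% to 5.7-11.3%.

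**5. Effect of the Part A gate on SPPB.** Section 3.2 justifies the two parts by limiting exposure until there is more evidence of benefit. Table 9-3 gives the chance of meeting both Part A criteria, and the title of Table 9-5 ties Part B power to the Part A outcome. The exact rule is blacked out, so assume that Part B opens only after success. With no effect on SPPB, false rejection at the end cannot exceed the Part A pass rate:

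- Significance alone: at most 2.5%. Simulation with 0.25 SD downward drift gives 1.5-2.0%.
- Significance and an estimate of at least 1 point, with 60 and 100 patients scaled by 265/339 to 46.9 and 78.2: the SE is SD·√(1/46.9 + 1/78.2) = 0.185·SD. At SD 1.5, 1/0.277 = 3.61, a pass rate of 0.015%. At SD 2.0, 1/0.369 = 2.71, a pass rate of 0.34%. Simulation gives about 0.01-0.3%.

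The 5.7-10.7% can then apply only to a secondary endpoint with no effect in a trial that has already succeeded on SPPB.

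**6. Price of a three-level period factor, no drift.** The information kept on 70 mg versus placebo is 72% (implied) to 89% (1:1:1:1). The SE grows by 1/√0.89 = 1.06 to 1/√0.72 = 1.18, so a comparison with 80% power falls to 75-66%. Trend power at 30 m and SD 70 m (linear/Emax/exponential) changes from 0.81/0.71/0.85 to 0.71/0.72/0.71 under the implied sizes, and from 0.86/0.80/0.89 to 0.82/0.80/0.84 at 1:1:1:1. Under an upward drift of 0.10 SD the pooled analysis has 0.73/0.67/0.77 (implied), about level with the factor.

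**The case for a change.** The best case for acting is that the layout is a fact and not a guess. Pooled arms from three differently allocated periods lose part of the protection of randomization. A baseline covariate cannot remove drift in effort or expectation after randomization. One factor is easy to add, and fixing it before interim results are known avoids a later post-hoc choice. The minimum trend power in Tables 9-6 and 9-8 would barely move if the contrasts were re-optimised.

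Much of this stands as general statistical reasoning: the period structure is real, and whoever writes the final model should consider it. It does not establish a fault in this protocol. Section 3.2 says which patients make up an arm, and a model with a period factor would combine them in just the same way. Nothing visible excludes that factor.

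The drift routes are also narrower than they first seem. At the interim analysis Table 16-1 keeps the patient, treating physician, investigator and blinded monitor blinded. Section 9.8 has an independent team run that analysis. Section 5.4 keeps those who administer the assessments blinded throughout. Effort-based scoring happens with these people, not with the sponsor roles that may see group-level results.

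**Conclusion.** The concern does not hold. The allocation pattern and the arithmetic are right, but the step from pooled planning tables and a sentence about combining data to a missing model term is not supported. The text that would settle it is not visible, and the choice of model factors commonly belongs in the statistical analysis plan.

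The size of the risk depends on a drift that the protocol does not give. At an assumed 0.25 SD downward, the ungated trend error is 5.7-10.7%. For SPPB it is at most 2.5%, and about 0.01-0.3% if both Part A criteria must be met. Against this, the factor costs 11-28% of the information on low dose versus placebo and, under the implied sizes, about 10 points of trend power for the linear shape and 14 for the exponential. It roughly breaks even on power near an upward drift of 0.10 SD. Either choice is defensible in a Phase II dose-finding study whose low-dose pairwise tests are supportive and unadjusted.

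These figures assume 18 patients per arm before v02, 265 analysed of 339, the Part B ratios shown, additive drift and, for the SPPB bound, a Part B that opens only after Part A succeeds.

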3.3 Rationale for dose/regimen, duration of treatment

3.3.1 Dose and frequency

[figure not shown]
Part A of the study will evaluate the fixed i.v. dose of 700 mg bimagrumab administered every 4 weeks over a 20-week period for a total of six doses.

Part B of the study will evaluate fixed i.v. doses of 70 mg, 210 mg, or 700 mg bimagrumab every 4 weeks over a 21-week period for a total of six doses.

[figure not shown]
[figure not shown]
[REDACTED]

Fixed i.v. dosing rather than body weight based dosing will be used in the current study [REDACTED], allowing the exploration of dose-exposure-response relationship estimation and supporting final dose selection and

subsequent clinical development of bimagrumab for patients with sarcopenia. Based on the definition of sarcopenia and experience in this and prior studies, the lower limit of body weight has been lowered by 5 kg to 35 kg to be more inclusive of older adults in Asian countries. It is unlikely that a person will weigh more than 100 kg based on the limits of ASMI and BMI.

Exposure to bimagrumab for 6 monthly doses is expected to be safe and well tolerated based on the experience from earlier clinical studies.

However, future clinical experience with bimagrumab may clarify more precisely where the limits of efficacy and tolerability are. Therefore, this study proposes to investigate a wider rather than narrower range of bimagrumab exposures by administering a fixed dose of 700 mg, 210 mg and 70 mg.

Six doses will be used to evaluate the durability of treatment on the expected improvement in physical function and the time course for multiple performance assessments and to avoid

being misled by early changes that are not maintained with continued dosing ([Papanicolaou et al 2013](#)).

3.4 Rationale for choice of comparator

A placebo infusion will be used as the comparator in this placebo-controlled study; no drug comparator will be used. A placebo is used because several of the outcome measures are behavioral in nature and dependent on a patient's or observer's beliefs and perceptions. Therefore, knowing treatment assignment may bias outcome measures and other important results (i.e., AEs). In addition, placebo-controlled studies provide the optimal situation to distinguish adverse events caused by a drug from those resulting from underlying conditions or "background noise". As there is no approved pharmacotherapy for sarcopenia and it is not known if bimagrumab is efficacious, the use of placebo is ethically appropriate.

3.5 Purpose and timing of interim analyses/design adaptations

An interim analysis is planned to evaluate the efficacy and safety of multiple doses of bimagrumab in patients with sarcopenia. [REDACTED]

[REDACTED] The analysis will assess the effect of bimagrumab by the change from baseline to week 25 for efficacy in SPPB total and component scores, 6MWT distance and [REDACTED]. Safety will also be examined based on the incidence of adverse events and clinically relevant changes in certain clinical laboratory variables.

[REDACTED]

[figure not shown]
[figure not shown]
[figure not shown]
[REDACTED]

[figure not shown]
Further information is described in [Section 9.8](#).

[figure not shown]
3.6 Risks and benefits

Target related risks and selection of participants

[figure not shown]
A paucity of human data limits the ability to predict the short and long-term risk of reducing the activity of myostatin and other ActRII ligands in older adults. However, the risk to patients in this trial will be minimized by adherence to the inclusion/exclusion criteria and close clinical monitoring.

[figure not shown]
[figure not shown]

An external Data Monitoring Committee (DMC) will monitor safety data from the study and currently monitors the entire bimagrumab program for potential safety concerns (see [Section 8.4](#)).

